4 PROTOCOL AMENDMENTS

Modification of the protocol is prohibited without prior written agreement in the form of a protocol amendment. All amendments must be created by the study sponsor and must be approved by the IRB/IEC and global and regional health authorities, as applicable, prior to implementation except when required to mitigate immediate safety risks or when the changes involve only logistical or administrative revisions.

Amendments may necessitate that the informed consent and other study-related material be revised. If the consent form is revised, all subjects currently enrolled in the study must sign the approved, revised informed consent (re-consent), as required by the IRB/IEC.

Refer to Appendix A for detailed description of amendments.

5 INTRODUCTION

5.1 Rationale and Background

The investigational contact lens (Alcon serafilcon A) is intended for the optical correction of refractive ametropia in persons with nondiseased eyes. This study will evaluate the on-eye clinical performance of investigational Alcon serafilcon A contact lenses compared against marketed ACUVUE[®] OASYS with HYDRACLEAR[®] PLUS Technology contact lenses to evaluate product performance in the intended population, when worn on a daily wear modality.

ACUVUE[®] OASYS with HYDRACLEAR[®] PLUS Technology contact lenses were chosen as the comparator product because these lenses also are reusable contact lenses (see Package Insert for ACUVUE[®] OASYS with HYDRACLEAR[®] PLUS Technology contact lenses). The intended use of this contact lens is vision correction; therefore, the measurement of distance VA is planned as the primary effectiveness endpoint.

5.2 **Purpose of the Study**

The purpose of this study is to assess the clinical performance of the investigational Alcon serafilcon A contact lenses as compared to marketed ACUVUE[®] OASYS with HYDRACLEAR[®] PLUS Technology contact lenses. The primary objective of this study is to demonstrate noninferiority in the visual acuity at distance when wearing Alcon serafilcon A contact lenses compared to ACUVUE[®] OASYS with HYDRACLEAR[®] PLUS Technology

contact lenses when worn on a daily wear modality.

At the end of the study, a clinical study report will be prepared in accordance with applicable regulatory requirements and standards.

5.3 **Risks and Benefits**

The clinical investigation process risks are managed through appropriate training and monitoring according to the protocol specific monitoring plan. Investigational device risks, including risks associated with use of device and methods and procedures for application of device, are defined in the investigator's brochure and/or product labeling and are managed through review of safety assessments outlined in this protocol.

Contact lenses may offer improved peripheral vision and the convenience of not wearing spectacles. Material properties and design characteristics of the test contact lens are features consistent with successful contact lens wear.

The Alcon serafilcon A contact lenses and AOHP contact lenses can be worn on daily wear modality until the end of their respective wear cycles.

A summary of the known potential risks and benefits associated with the investigational Alcon serafilcon A contact lens can be found in the investigator's brochure (see Package Insert for AOHP contact lenses). Risks are minimized by compliance with the eligibility criteria and study procedures, and through close supervision by a licensed clinician during exposure to the study lenses. The potential harms associated with on-eye exposure to the new lens materials include toxicity response, blurred vision, and ocular discomfort. In general, the risks with the investigational contact lens are anticipated to be similar to other marketed soft contact lenses. The site personnel will educate subjects on proper hygiene and lens handling, and compliance with the use of contact lenses according to the protocol. Subjects should be instructed not to wear contact lenses while sleeping or swimming. The site personnel will also advise the subjects to remove contact lenses and return for prompt follow-up of symptoms, such as ocular discomfort, foreign body sensation, excessive tearing, vision changes, or hyperemia.

There may also be unknown risks to use of test product. Any risk to subjects in this clinical study will be minimized by compliance with the eligibility criteria and study procedures, clinical oversight, and monitoring

Refer to the IB for additional information.

6 STUDY OBJECTIVES

[figure not shown]
6.1 **Primary Objective(s)**

Table 6–1Primary Objective(s)

Objective(s)	Endpoint(s)
The primary objective of this study is to demonstrate noninferiority in the visual acuity at distance when wearing Alcon serafilcon A contact lenses compared to AOHP contact lenses when worn in a daily wear modality.	• Distance visual acuity (logMAR) with study lenses at Week 1

6.2 Secondary Objective(s)

Not Applicable.

[figure not shown]
6.4 Safety Objective(s)

Objective(s)	Endpoint(s)
Describe the safety profile of the study products.	Adverse eventsBiomicroscopy findings
	Device deficiencies

7 INVESTIGATIONAL PLAN

7.1 Study Design

This will be a multisite, prospective, randomized, double masked, bilateral, crossover study comparing 2 reusable soft contact lenses. The expected duration of subject participation in the study is approximately 28 days (~14 days per each lens type), with 7 scheduled visits. Subjects will be asked to wear their habitual spectacles only (no contact lens wear) during the washout periods for 2 (at least 48 hours) to 4 days after Visit 1 and after Visit 4.

7.2 Rationale for Study Design

This study design is justified based upon an evaluation of the results of relevant preclinical and clinical testing, as described within the IB.

The investigational contact lens is intended for the optical correction of refractive ametropia in persons with nondiseased eyes.

The purpose of this study is to assess the clinical performance of the investigational Alcon serafilcon A contact lenses as compared to marketed AOHP contact lenses.

Procedures for measurement were selected based on common practice for these assessments. The design of this study is justified based upon preclinical and clinical testing, as described within the investigator's brochure.

AOHP contact lenses were chosen as the comparator product because these lenses also are reusable contact lenses (see Package Insert for AOHP contact lenses).

The intended use of this contact lens is vision correction; therefore, the measurement of distance VA is planned as the primary effectiveness endpoint.

The crossover design will ensure that the same subject is exposed to both the test and comparator lens materials;

The study will only include normal **contact** lens wearers to ensure the subjects participating in this trial represent the average clinic population and a population that can detect differences between lens materials. The study will exclude any current/habitual AOHP lens and daily disposable contact lens wearers, and any previous wearers of AOHP lens in the past 6 months prior to consent and any previous daily disposable contact lens wearers in the past 3 month prior to consent in order to reduce potential bias of wearers to their habitual contact lenses.

7.2.1 Purpose and Timing of Interim Analyses and Resulting Design Adaptations

Interim analysis will not be performed.

7.3 Rationale for Duration of Treatment/Follow-Up

Subjects will wear each study product bilaterally for their respective wear cycles on a daily wear modality.

. The lenses will be provided by a qualified unmasked study staff member in such a manner that the subject and the investigator remain masked to the lens type.

7.4 Rationale for Choice of Comparator Product

AOHP contact lenses were chosen as the comparator product because these lenses also are reusable contact lenses (see Package Insert for AOHP contact lenses).

7.5 Data Monitoring Committee

Not applicable.

8 STUDY POPULATION

Volunteer subjects aged 18 or over who are habitual spherical soft contact lens wearers (excluding current/previous ACUVUE[®] OASYS with HYDRACLEAR[®] PLUS Technology habitual lens wearers and daily disposable lens wearers), have at least 3 months of contact lens wearing experience, and who wear their habitual lenses at least 5 days per week and at least 8 hours per day.

One specific group of subjects will be recruited for this study: normal contact lens wearers.

The study population includes approximately 185 volunteer subjects to be enrolled at approximately ~14 sites, with approximately 14 subjects enrolled per site. The study population will consist of subjects with normal eyes (other than the need for optical correction for myopia), who are adapted, existing wearers of soft contact lenses in both eyes for at least the past 3 months and who wear contact lenses at least 5 days per week and at least 8 hours per day.

8.1 Inclusion Criteria

Written informed consent must be obtained before any study specific assessment is performed. Upon signing informed consent, the subject is considered enrolled in the study

Subjects eligible for inclusion in this study must fulfill all of the following criteria:

- 1. Subject must be at least 18 years of age.
- 2. Subject must be able to understand and must sign an informed consent form (ICF) that has been approved by an Institutional Review Board (IRB).
- 3. Successful wear of spherical soft contact lenses in both eyes for a minimum of 5 days per week and 8 hours per day during the past 3 months.
- 4. Manifest cylinder of \leq -0.75 D in each eye.
- 5. Best corrected visual acuity (BCVA) 20/25 Snellen (0.10 logMAR) or better in each eye.
- 6. Subject must possess spectacles and be willing to wear habitual spectacles for vision correction when study lenses are not worn, as needed.
- 7. Subject must be willing to stop wearing their habitual contact lenses for the duration of study participation.
- Able to wear contact lenses within a range of sphere power from -1.00 D to -6.00 D (0.25 D steps) and subject willing and able to wear the study lenses for the full duration of the study.
- 9. Subject must be willing to wear contact lenses for at least 16 hours per day on the day prior to week 1 and on the day prior to week 2 follow up visits for both test and comparator lenses.

10. Subject must be able to be successfully fit with test and comparator lenses.

8.2 Exclusion Criteria

Subjects fulfilling any of the following criteria are not eligible for participation in this study.

- 1. Any anterior segment infection, inflammation, or abnormality or disease (including systemic) that contraindicates contact lens wear, as determined by the investigator.
- 2. Any use of systemic or ocular medications for which contact lens wear could be contraindicated, as determined by the investigator.
- 3. History of refractive surgery or plan to have refractive surgery during the study or irregular cornea in either eye.
- 4. Ocular or intraocular surgery (excluding placement of punctal plugs) within the previous 12 months or planned during the study.
- 5. Biomicroscopy findings at screening that are moderate (Grade 3) or higher and/or corneal vascularization that is mild (Grade 2) or higher; presence of corneal infiltrates.
- 6. Current or history of pathologically dry eye in either eye that, in the opinion of the investigator, would preclude contact lens wear.
- 7. Current or history of herpetic keratitis in either eye.
- 8. Eye injury in either eye within twelve weeks immediately prior to enrollment for this trial.
- 9. Current or history of intolerance, hypersensitivity, or allergy to any component of the study products.
- 10. Wearing habitual contact lenses in an extended wear modality (routinely sleeping in lenses for at least 1 night per week) over the last 3 months prior to enrollment.

- 11. Any use of topical ocular medications and artificial tear or rewetting drops that would require instillation during contact lens wear.
- 12. The investigator, his/her staff, family members of the investigator, family members of the investigator's staff, or individuals living in the households of the aforementioned persons may not participate in the study.
- 13. Participation of the subject in a clinical trial within the previous 30 days or currently enrolled in any clinical trial.
- 14. Habitual AOHP contact lens wearers and current habitual wearers of any daily disposable contact lenses.

16. Currently pregnant, as stated by the subject

8.3 Rescreening of Subjects

Rescreening of subjects is not allowed in this study.

9 TREATMENTS ADMINISTERED

9.1 Investigational Product(s)

Test Product(s):	Alcon serafilcon A contact lenses	
Comparator Product(s) (If	ACUVUE [®] OASYS with HYDRACLEAR [®] PLUS	
applicable):	Technology contact lenses	

Table 9–1Test Product

Test Product	Alcon serafilcon A contact lenses
Manufacturer	Alcon Laboratories, Inc.
	[name]
	USA
Indication for use	The investigational contact lens is intended for the optical
and intended	correction of refractive ametropia in persons with nondiseased eyes.

purpose in the		
current study		
Product description	Material - serafilcon A	
and parameters	• Water content $55 \pm 2\%$	
available for this	• Power range: -1.00 to -6.00 D in 0.25 steps	
study	• Base curve (mm): 8.4 mm	
	• Diameter (mm): 14.2 mm	
Usage	• Wear:	
	• Daily Wear	
	• Bilateral	
	• Replacement lenses will not be provided to the subject. In the	
	event a lens needs to be replaced, the subject must return to the	
	site for a replacement lens. Until the replacement lens is	
	obtained, the subject must store both study lenses in the	
	provided lens care solution and wear their habitual spectacles.	
	• Exposure: Study lenses are to be worn during typical contact	
	lens wearing hours, on all days during the study lens wearing	
	period, at least 10 hours per day, over each treatment period (7	
	days (-0/+1) according to randomization assignment). Subjects	
	will be asked to wear their study lenses for 16 hours on the days	
	prior to each Follow-up Visit (Visit 3, 4, 6, & 7).	
	• Lens Care: Cleaned and disinfected with CLEAR CARE [®]	
	Cleaning & Disinfecting Solution after each use.	
Number/Amount of	Provided in bags of (25) lenses per power per bag	
product to be		
provided to the site		
Dealraging		
Packaging	Blister foil pack	
description		

Labeling description	Lens Foil label includes:	
	- material name and identifier	
	- base curve	
	- diameter	
	- manufacturing protocol number	
	- packing solution	
	- power	
	- lot number	
	- expiration date	
	- content statement	
	- investigational device statement	
	- sponsor information	
Storage conditions	Store at room temperature.	
Lens Care	Cleaned and disinfected with CLEARCARE [®] Cleaning &	
	Disinfecting Solution after each use.	
Supply	Refer to the MOP for a detailed description	

Table 9–2	Comparator Product
Comparator Product(s)	ACUVUE [®] OASYS with HYDRACLEAR [®] PLUS Technology contact lenses
Manufacturer	Johnson & Johnson Vision
Indication for Use	The comparator contact lens is intended for the optical correction of refractive ametropia in persons with nondiseased eyes
Product description and parameters available for this study	 Material: senofilcon A Water content: 38% Power range: -1.00 to -6.00 D in 0.25 steps Base curve (mm): 8.4 mm and 8.8 mm Diameter (mm): 14.0 mm
Formulation	See package insert for AOHP contact lenses
Usage	• Wear:

Number/Amount of Product to be Provided to the	 Daily Wear Bilateral Replacement lenses will not be provided to the subject. In the event a lens needs to be replaced, the subject must return to the site for a replacement lens. Until the replacement lens is obtained, the subject must store both study lenses in the provided lens care solution and wear their habitual spectacles. Exposure: Study lenses are to be worn during typical contact lens wearing hours, on all days during the study lens wearing period, at least 16 hours a week, over each treatment period (14 day (-0/+1) according to randomization assignment). Subjects will be asked to wear their study lenses for 16 hours a week prior to each Follow-up Visit (Visit 3, 4, 6, & 7). Lens Care: Cleaned and disinfected with CLEAR CARE[®] Cleaning & Disinfecting Solution after each use. Each Site will procure their own comparator lenses.
subject Packaging	Provided in commercial packaging
description	
Labeling description	Commercial foil.
Storage conditions	Store at room temperature
Lens Care	Cleaned and disinfected with CLEAR CARE [®] Cleaning & Disinfecting Solution after each use.
Supply	 Refer to the MOP for a detailed description Each site will procure their own comparator lenses. CLEAR CARE[®] contact lens solution supplied by sponsor to be provided to the subject

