10.2.3 Investigational Product Compliance

Review subject compliance with the IP usage and adjunct product usage and collect all used and unused study IPs and other products that were dispensed.

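### Table 9-2 sets comparator wear at 16 hours a week, where Table 9-1 sets test wear at 10 hours a day

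*Protocol*

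**What the plan says.** The Usage rows of the two product tables in section 9.1 each carry an Exposure instruction.

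- **Table 9-1 (test):** wear on all days, "at least 10 hours per day, over each treatment period (7" days). Before the follow-up visits, subjects "will be asked to wear their study lenses for 16 hours on the days" preceding Visits 3, 4, 6 and 7.
- **Table 9-2 (comparator):** wear "on all days during the study lens wearing period, at least 16 hours a week", over a treatment period given as 14 days. Before the visits: "Subjects will be asked to wear their study lenses for 16 hours a week prior to each Follow-up Visit", again naming Visits 3, 4, 6 and 7.

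Four other places bear on these cells:

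- **Section 8.1, criterion 9** requires willingness to wear lenses for at least 16 hours on the day before the Week 1 visit and "on the day prior to week 2 follow up visits for both test and comparator lenses".
- **Section 10.2.3** tells sites to "Review subject compliance with the IP usage and adjunct product usage".
- **Section 9.4** describes two treatment periods of two weeks each.
- **Section 7.3** states: "Subjects will wear each study product bilaterally for their respective wear cycles on a daily wear modality".

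**The concern.** The two cells are parallel instructions for the two arms of a crossover, yet one is a daily minimum and the other a weekly minimum that is far lower. Sections 7.2 to 7.4 give no reason for a lower comparator standard. The pre-visit sentence of Table 9-2 also fails to ask for the 16-hour day that criterion 9 expects with both lenses. The weekly minimum taken alone does not conflict with criterion 9.

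Two things are at stake.

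- **Compliance.** Section 10.2.3 has sites review product usage, and these rows are where the protocol states that usage. The same wearing behaviour could be a deviation with one lens and acceptable with the other. Whether this would reach the per protocol set depends on the Deviations and Evaluability Plan, which is not shown.
- **The primary comparison.** The endpoint is distance visual acuity at Week 1. If the tables were followed literally, wear before that visit would go with lens in both sequences. The period and sequence terms of the model in section 12.4.1.2 could not remove it, because it would be aliased with the lens effect.

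The same cells also give the treatment period as 7 days (test) and 14 days (comparator), and the 7-day figure does not match the two-week periods of section 9.4.

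**Working it through.** **Inputs**

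- Test minimum: 10 h/day (Table 9-1).
- Comparator minimum: 16 h/week (Table 9-2).
- Pre-visit day: 16 h (Table 9-1 and criterion 9).
- Week 1 visit: 7 days after dispensing, window -0/+1 (section 10).
- Assumption: actual comparator wear of 8 to 10 h/day plus a 16-hour pre-visit day. The lower end is the habitual-wear eligibility floor in criterion 3, "for a minimum of 5 days per week and 8 hours per day during the past 3 months". The upper end is the test-lens minimum. Neither is a forecast made by the protocol.

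**Step 1. Literal minimums over 7 wear days**

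- Test: 7 × 10 = 70 h, or 6 × 10 + 16 = 76 h with the pre-visit day.
- Comparator: 16 h. Spread over all 7 days this is 16 / 7 = 2.3 h/day, against 10 h/day.
- Ratio of the stated weekly minimums: 70 / 16 = 4.4.

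These are floors, not expected wear.

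**Step 2. Plausible wear to Week 1, test lens at its stated minimum**

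| Visit | Test | Comparator at 8 h/day | Comparator at 10 h/day |
|---|---|---|---|
| 7 wear days | 6 × 10 + 16 = 76 h | 6 × 8 + 16 = 64 h | 6 × 10 + 16 = 76 h |
| 8 wear days | 7 × 10 + 16 = 86 h | 7 × 8 + 16 = 72 h | 7 × 10 + 16 = 86 h |

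- 7 days: ratio 76 / 64 = 1.19 down to 76 / 76 = 1.00; difference 12 h down to 0 h.
- 8 days: ratio 86 / 72 = 1.19 down to 86 / 86 = 1.00; difference 14 h down to 0 h.

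**Step 3. One wear pattern judged under both rules**

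Take 8 h on six days and 16 h on the day before the visit, 64 h in all.

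- Under Table 9-1, six of the seven days fall below 10 h, so the pattern is non-compliant.
- Under Table 9-2, 64 / 16 = 4.0, so it meets the weekly minimum four times over.

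**Step 4. Which reading is likely**

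Both cells speak generically of study lenses and list all four follow-up visits, although a subject wears a given lens at only two of them. This suggests one common text that was altered in one table. The weekly wording occurs twice in Table 9-2, in complete sentences, so it is unlikely to be a fault of text extraction. It also sits poorly with the same cell's requirement of wear on all days in typical hours.

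**Step 5. The period lengths**

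The 7-day and 14-day figures may be replacement cycles under the wrong label, since section 7.3 refers to a separate wear cycle for each product. The text does not settle this, and the two figures need not be equal.

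**The case against.** The strongest reply has four parts.

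1. **Table 9-1 already covers both lenses.** Its wording is generic and its visits span both periods, so the 10-hour and 16-hour rules could be read as applying to the comparator too. This supports a drafting error. It does not remove the contradiction, because Table 9-2 is equally generic and both lenses would then be under two rules.
2. **The rules are looser and stricter, not incompatible.** A subject who wears lenses 10 hours a day also exceeds 16 hours a week, and a 16-hour pre-visit day satisfies both pre-visit sentences. That is correct: one behaviour can meet both. But a site or subject working from Table 9-2 is not told to do what criterion 9 presumes.
3. **Masking makes two standards unlikely in practice.** Subjects and investigators do not know the lens, so they could hardly apply lens-specific wear targets. This stands as a reason to expect little effect. It is also a reason to have a single rule, since different targets by period could hint at lens identity.
4. **The consequences are not demonstrated.** Section 10.2.3 does not cite the two tables, and the manual of procedures and the evaluability plan may set working criteria. The 1.19 ratio puts test wear at its floor and comparator wear below it, although the same people wear both lenses. All of this stands. It limits the size of the problem, not its existence.

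**Conclusion.** The point holds. Table 9-2 is wrong as written: its wear minimum differs from that of Table 9-1 without a stated reason, and its pre-visit sentence does not agree with criterion 9. It is very probably a drafting error.

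The gap in the literal minimums is large, about 4.4-fold per week, but subjects are habitual wearers told to wear lenses on all days in typical hours. On the assumed 8 to 10 h/day for the comparator, the wear ratio to Week 1 is 1.00 to 1.19. No effect on visual acuity can be calculated, because the protocol relates wear time to acuity nowhere. Any bias is therefore of unknown size and direction and probably small, and any effect on the per protocol set depends on a plan that is not shown.

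It should still be corrected. This is an operative instruction for product use, section 14 requires adherence to the protocol and bars waivers, and the remedy costs almost nothing.

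**What to change.** Amend the Exposure text of Table 9-2 to a minimum of 10 hours per day and 16 hours on the day before each follow-up visit, in line with Table 9-1 and criterion 9. Use that one rule for subject instructions and for compliance review with both lenses. If the 7-day and 14-day figures are replacement cycles, keep them but label them so, and leave the two 2-week treatment periods of section 9.4 as they are.

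The cost is a wording change in one table cell, plus a relabel of the day counts if needed. No subjects, visits or procedures are added. With the change, both lenses have the same minimum to Week 1: 70 h over 7 wear days, or 76 h counting the pre-visit day.
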